3.1.1 Primary efficacy variable

The primary efficacy variable is the annualized rate of change in mean of the maximum (MeanMax) CIMT measurements from each of the 12 carotid artery sites based on all scans performed during the 104-week study period. The maxCIMT value for each site will be the dependent variable in mixed effects model.

3.1.2 Secondary efficacy variables

The secondary outcome variables are

- Annualized rate of change in the MeanMax CIMT of the near and far walls of the right and left CCA, using maxCIMT value from CCA as the dependent variable.
- Annualized rate of change in the MeanMax CIMT of the near and far walls of the right and left carotid bulb, using maxCIMT value from carotid artery bulb as the dependent variable.

- Annualized rate of change in the MeanMax CIMT of the near and far walls of the right and left ICA, using maxCIMT value from ICA as the dependent variable.
- Annualized rate of change in the mean of the mean (MeanMean) CIMT of the near and far walls of the right and left CCA, using meanCIMT value from CCA as the dependent variable.
- Percentage change from baseline to final visit in low-density lipoprotein cholesterol (LDL-C) (using converted results – see section 4.1), total cholesterol, high-density lipoprotein cholesterol (HDL-C), triglycerides (TG), non-HDL-C, apolipoprotein (Apo) B, ApoA-I, non-HDL-C/HDL-C, and ApoB/ApoA-I

Please refer to Appendix B for description of efficacy objectives and outcome variables corresponding to each objective.

3.2 Safety and tolerability

No formal statistical testing of the safety and tolerability variables will be carried out. The safety and tolerability variables will be individually summarized using the safety analysis set. The safety and tolerability variables are:

- Adverse events (AEs)
- Serious adverse events (SAEs)
- Changes in clinical laboratory values (hematology, chemistry, and urinalysis)
- 12-lead electrocardiograms (ECGs)
- Vital signs
- Physical examinations

4. ANALYSIS METHODS

4.1 General principles

All statistical evaluation, as well as summaries and tabulations will be done by qualified personnel at IQVIA. Before breaking the treatment codes, following clean file declaration, all decisions made on the evaluability of the data for each individual subject will be documented and each subject will be assigned to the appropriate analysis data set.

The primary analysis for efficacy variables will be based on the ITT analysis set. The CIMT analysis will be performed on the PP population as a robustness check of the analysis on ITT analysis set.

A multilevel, repeated measures, linear mixed effects model will be used for the analysis of the primary and secondary CIMT end points. Rationale for the choice of the model follows Espeland et al (1992 and 1999) and Pitt et al (2000). Details of the model are given in section 4.3.3.

No multiplicity adjustment will be applied to the secondary efficacy analysis.

Lipid and Apo analyses will be performed on the ITT analysis set only. The definition of baseline for laboratory endpoint variables is given in section 4.1.1.

Secondary lipid and lipoproteins outcome measures are the percentage change from baseline, which will be analyzed by analysis of covariance (ANCOVA) with terms for treatment as a factor and baseline value as a covariate in the model. For lipid measurements (LDL-C, total cholesterol, HDL-C, TG, non-HDL-C, non-HDL-C/HDL-C), both the analysis of the percent change from baseline at final visit, and the analysis of the percent change from baseline to time-weighted average during treatment will be performed. In the evaluation of change from baseline to final visit, missing observations will be imputed by last observation carried forward (LOCF) method. No imputation will be made for missing lipid values for time-weighted average analysis.

During the study, LDL-C measurement was transitioned from 2nd generation reagent to 3rd generation reagent by direct assay. Post-baseline LDL-C values will be affected. To evaluate the consistency of different measurement reagents, all post-baseline LDL-C related analysis will be performed on two sets of data.

- LDL-C values as collected, regardless of the type of reagent.
- LDL-C converted, where values which used 3rd generation reagent (i.e. all values collect on or after the 8th March 2018) are converted to 2nd generation values using the formula $X=0.0626+0.882*Y$, where X is the LDL-C value (in SI units, mmol/L) using 3rd generation reagent, Y is the LDL-C value using 2nd generation reagent. (see [Appendix E](#) for details).

For Apo measurements (ApoB, ApoA-I, ApoB/ApoA-I), the analysis of the percent change from baseline to final visit (LOCF) will be performed.

Statistical significance will be set at $\alpha=0.05$

The day of first dose of double-blind study medication (day 1) will be defined as the reference start date for the randomized treatment period and will be displayed in the listings where an assessment date or event date appears when appropriate.

- If the date of the event is on or after the reference date, then: Study Day = (date of event – reference date) + 1.

- If the date of the event is prior to the reference date, then: Study Day = (date of event – reference date).

Duration of an event is calculated as stop date-start date + 1. For example, time on treatment (days) = Date of last dose - date of first dose + 1.

No analysis visit windows will be derived. All by-visit data will be presented by protocol scheduled nominal visits. Listings will include unscheduled visits.

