4.3.5 Laboratory data

Analyses of percentage change from baseline in lipids and lipoproteins will be carried out for the ITT population using ANCOVA with terms for treatment and baseline value as a covariate in the model. For LDL-C, this will be analysed for both sets of LDL-C values (collected and converted) described in section 4.1. However, the converted values will be considered as the secondary endpoint while the collected values will be used for supportive analysis.

The assumptions of normality and homogeneity of variance will be explored using probability and residual plots. If assumptions are found to be violated, rank ANCOVA approach (Quade 1967) will be used.

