4.5.1 Summary of laboratory variables over time

Descriptive statistics (number of observations, mean, SD, minimum, median and maximum values) for collected values, change from baseline, and percentage change from baseline will be summarized for clinical laboratory tests (hematology, chemistry, urinalysis, lipid profile) at each protocol scheduled nominal visit and at the last non-missing post-baseline visit, across treatment groups.

Hepatic biochemistry and CK values as well as their changes from baseline, plus change from baseline and percentage change from baseline in creatinine, will be summarised using descriptive statistics at each visit.

Hematology, hepatic biochemistry (including CK) and clinical chemistry values outside the laboratory reference ranges will be flagged and summarised.

Urinalysis data including pH and specific gravity will be summarised by mean, median, SD, minimum, maximum, and number of subjects for each treatment group at each visit.

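### Running the LDL-C analyses on as-collected and converted values shows sensitivity to the reagent conversion, not whether the conversion holds in this trial; a reagent-period check on observed week 104 samples would

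*SAP*

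**What the plan says.** SAP 4.1 (General principles) reports that direct LDL-C measurement moved from a 2nd- to a 3rd-generation reagent during the study, and adds: "Post-baseline LDL-C values will be affected". The response is: "To evaluate the consistency of different measurement reagents, all post-baseline LDL-C related analysis will be performed on two sets of data".

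- The first set is "LDL-C values as collected, regardless of the type of reagent".
- The second set converts the later values ("all values collect on or after the 8th March 2018") to the 2nd-generation scale with X = 0.0626 + 0.882 × Y, "where X is the LDL-C value (in SI units, mmol/L) using 3rd generation reagent, Y is the LDL-C value using 2nd generation reagent".

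SAP 4.3.5 ranks the two sets: "the converted values will be considered as the secondary endpoint while the collected values will be used for supportive analysis". The ANCOVA in SAP 4.1.5 and Appendix C has treatment and baseline only. SAP 4.1.6 computes the time-weighted average on both sets. SAP 4.3.8 uses converted values only. SAP 4.5.1 summarises "clinical laboratory tests (hematology, chemistry, urinalysis, lipid profile) at each protocol scheduled nominal visit", lipids included, with no split by reagent. Appendix E is titled as a method comparison of the two reagents, but its content is an embedded file that cannot be read here.

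**The concern.** The aim given to the pair of data sets is to evaluate reagent consistency. Both sets contain the same measurements, and the second is a deterministic function of part of the first. Whatever gap appears between their results was fixed by the equation once the sample dates were known. A right equation and a wrong one would each produce such a gap, and nothing planned tells them apart.

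This matters for two reasons. The LDL-C secondary endpoint rests on the conversion for a large share of final values. And the as-collected results, including by-visit tables, contain a late step that comes from the assay. Without a reagent split, that step could be read as real drift on placebo or as disagreement with the main result.

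**Working it through.** The documents state no size for the reagent shift, so there is no figure to reproduce beyond the equation itself.

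**1. What the two sets can show.** Let Z be a recorded value, g = 1 if it was taken on or after 8 March 2018, and c( ) the conversion. Percent change differs between the sets by 100 × g × [c(Z) − Z] / baseline. Every term is known without reference to what the other reagent would have read in that sample, so the difference carries no evidence about c( ).

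**2. Step per post-switch sample.** As printed, 3rd = 0.0626 + 0.882 × 2nd. With labels swapped, 3rd = (2nd − 0.0626)/0.882. The levels are the entry limits in Protocol 3.1 (3.1, 4.1, 4.9 mmol/L), the 70 mg/dL cut-off in SAP 4.3.8 (about 1.81 mmol/L), and an assumed typical baseline of 3.6.

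| 2nd-generation LDL-C (mmol/L) | 3rd, as printed | Change | 3rd, labels swapped | Change |
|---|---|---|---|---|
| 1.81 | 1.659 | −8.3% | 1.981 | +9.5% |
| 3.1 | 2.797 | −9.8% | 3.444 | +11.1% |
| 3.6 | 3.238 | −10.1% | 4.011 | +11.4% |
| 4.1 | 3.679 | −10.3% | 4.578 | +11.6% |
| 4.9 | 4.384 | −10.5% | 5.485 | +11.9% |

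**3. Share of samples affected.** Protocol 9.3 expects the study to run from 3Q 2015 to 1Q 2019. With 104 weeks (728 days) of treatment, randomisation ends by about 1Q 2017, so baselines precede the switch. Assume uniform accrual. The share at week 104 is (days from 8 March 2018 to the last subject's week 104) / (accrual days):

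- 1 Jul 2015 to 1 Jan 2017: 297/550 = 54%
- 1 Jul 2015 to 31 Mar 2017: 386/639 = 60%
- 30 Sep 2015 to 1 Jan 2017: 297/459 = 65%
- 30 Sep 2015 to 31 Mar 2017: 386/548 = 70%

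At week 39 the share is 0% in all four cases. Early terminations and LOCF would lower the share among final values.

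**4. Effect on the as-collected results.** Take a share p = 0.60.

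- Placebo with no true change from 3.6 mmol/L: 0.60 × (−10.1%) = about −6 points. Labels swapped: 0.60 × 11.4% = about +7 points.
- Arm difference: the intercept is common to both arms, so the difference is multiplied by 1 − p × (1 − 0.882) = 1 − 0.60 × 0.118 = 0.929, about 7% smaller (6.4% at p = 0.54, 8.3% at p = 0.70). Labels swapped: 1 + 0.60 × (1/0.882 − 1) = 1.080, about 8% larger.

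A simulation of the SAP's ANCOVA agrees. It used 543 subjects randomised 1:1, p = 0.60, and the following assumptions: baseline mean 3.6 and SD 0.4 mmol/L, 15% log-scale noise, 40% lowering on rosuvastatin. With labels as printed:

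| | One reagent scale | As collected |
|---|---|---|
| Placebo mean change | +1.3% | −4.8% |
| Rosuvastatin mean change | −39.4% | −42.6% |
| Arm difference (points) | −40.6 | −37.8 |

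With labels swapped the difference moves from −40.4 to −43.6. With no true effect, rejection at the 0.05 level was 0.057 (as printed) and 0.053 (swapped). Adding a reagent main effect to the as-collected model gave −37.7 instead of −37.8; a treatment-by-reagent term picked up the rescaling, at about +4.6 points.

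**5. What a reagent-period check can detect.** With the labels as printed, the equation yields 3rd from 2nd generation, the reverse of the stated conversion, which would need Y = (X − 0.0626)/0.882. Suppose the printed form were applied to 3rd-generation values. A placebo subject at a true 3.6 reads 3.238 and is then 'converted' to 0.0626 + 0.882 × 3.238 = 2.918, or −18.9%. An assumed 45-point arm difference becomes 45 × 0.882² = 35.0 in that period and 0.40 × 45 + 0.60 × 35.0 = 39.0 overall. The planned comparison has no reference value that would expose this. In simulation, a reagent-period term on converted values showed a placebo step of about −19 points in every run; with the correct inverse the step was about 0.

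**The case against.** The strongest reply is that the plan already handles the switch. Converted LDL-C is the endpoint, the as-collected run is only supportive, and reporting raw values alongside converted ones is good practice. Validation belongs to Appendix E, which may hold paired-sample data. All of this stands, which is why the endpoint and the as-collected run should both stay. What remains is that the stated aim is not met, and that agreement in a method-comparison sample would not show that the conversion was applied correctly here.

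A reader might infer more than the documents support:

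- *The as-collected analysis was itself meant to establish consistency.* SAP 4.1 gives that aim to the two sets together.
- *The missing reagent term biases the treatment comparison.* A main effect barely moves the estimate, and randomisation balances calendar time, so rejection under no effect stays near 5%.
- *The conversion is unvalidated.* Appendix E cannot be read, so this cannot be said.

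An obvious check, comparing reagent periods on LOCF final values, is also open to a fair objection. Under Protocol 3.9, subjects with LDL-C at or above their limit on two consecutive visits stop treatment. Their high, early final values fall disproportionately before March 2018, so reagent at the final value is partly an outcome. With a perfect conversion, simulated false rejection ranged from 11% to 45% across the noise levels and standard errors tried. Restricting the check to observed week 104 samples, where the reagent is set by enrolment date, brought it back to about 5%. Case mix could still differ by enrolment date, so the check remains supportive.

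**Conclusion.** The point holds in a limited form. The two-set comparison is a sensitivity analysis to the conversion and cannot evaluate reagent consistency in these subjects. The as-collected results carry a step of roughly 8-12% per post-switch sample, affecting about 54-70% of week 104 samples. The supportive arm difference is rescaled by about 7% (smaller as printed, about 8% larger if the labels are swapped), and the placebo arm shows an artificial change of about 6-7 points. No false treatment effect arises, and the converted endpoint is in principle protected if the conversion is right and applied in the right direction.

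The shares rest on assumed uniform accrual within the expected calendar. The effect sizes rest on an assumed baseline near 3.6 mmol/L and 40-45% lowering. The sign depends on the formula's labels, which the documents leave unresolved.

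**What to change.** 1. In SAP 4.1 and 4.3.5, keep converted LDL-C as the secondary endpoint. Keep the as-collected run, but describe it as a sensitivity analysis to the conversion, and refer reagent agreement to Appendix E.
2. Add one supportive check on converted values, limited to subjects with an observed (not LOCF) week 104 sample. Fit percent change on baseline, treatment, reagent period (before, or on or after, 8 March 2018) and treatment-by-reagent, with robust standard errors. Report the placebo level and the treatment effect by period.
3. Split the as-collected by-visit LDL-C tables (SAP 4.5.1) by reagent.
4. Reconcile the direction and labels of the formula in SAP 4.1 with Appendix E, and print the form that will be programmed.

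The cost is SAP wording, one factor built from sample dates already held, and a few extra tables. The check is less precise within each period and should be read as supportive.

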4.1.6 Time weighted average lipid value

The time-weighted average lipid value is defined as the lipid value multiplied by the number of days since the last lipid assessment, summed for all lipid observations (this includes observations made at unscheduled visits), and divided by the sum of days between all visits. No imputation will be made for lipid missing values for the time-weighted average analysis.

$$\text{TWA} = \frac{x_1 t_1 + x_2 t_2 + \dots + x_n t_n}{t_1 + t_2 + \dots + t_n}, \text{ where}$$

x_i s are the lipid values measured at times $i=1, 2, \dots, n$, t_i s are the number of days between visit i and visit $(i-1)$.

And $T = t_1 + t_2 + \dots + t_n$ is the total number of days over which the assessments took place. This will be calculated for both sets of LDL-C values (collected and converted) described in section 4.1.

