4.3.4 Main and supportive between-group analyses of primary and secondary endpoints

Results from main analyses (based on ITT analysis set) will be considered definitive, and the purpose of supportive analyses (based on PP analysis set) is to demonstrate robustness of results from main analyses with different statistical models and in different subject populations. In the event that results from main and supportive analyses differ substantially further exploratory work will be carried out to explain the differences.

Primary Endpoint

The main analysis which gives a between-group assessment will be carried out using the mixed effects model as previously defined on subjects in the ITT analysis set population using maxCIMT data for all carotid artery sites.

A Supportive analysis will also be carried out in a similar way using only subjects in the PP population.

Secondary Endpoints

- MeanMax CCA CIMT

The main and supportive analyses will be as for the main and supportive analyses of the primary endpoint but using maxCIMT data only for sites in the CCA.

- MeanMax Bulb CIMT

The main and supportive analyses will be as for the main and supportive analyses of the primary endpoint but using maxCIMT data only for sites in the carotid artery bulb.

- MeanMax ICA CIMT

The main and supportive analyses will be as for the main and supportive analyses of the primary endpoint but using maxCIMT data only for sites in the ICA.

- MeanMean CCA CIMT

The main and supportive analyses will be as for the main and supportive analyses of the primary endpoint but using meanCIMT values measured in the CCA.

- Percentage change from baseline to final visit in LDL-C (converted values, see section 4.1), total cholesterol, HDL-C, TG, non-HDL-C, ApoB, ApoA-I, non-HDL-C/HDL-C, and ApoB/ApoA-I.

See section 4.3.5 for details.

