4.3.8 Exploratory analyses

Slope of the regression line, as defined in section 4.3.6, will be summarised (means, SD, N) for rosuvastatin treatment group only in each of the following subgroups (for only the converted LDL-C values, as described in section 4.1) to investigate the relevance of a reduction of LDL-C:

1. % change from baseline to time-weighted average during treatment in LDL-C: below and above or equal to the mean.
2. On-Treatment LDL-C (time-weighted average value):
 - below and above or equal to the mean
 - <100 mg/dL and \geq 100 mg/dL
 - <70 mg/dL and \geq 70 mg/dL
 - <70, (\geq 70- <100), and \geq 100 mg/dL
3. Loess plot of annualized rate of change in MeanMax CIMT in mm/year by % change in LDL-C and by on-treatment LDL-C (time-weighted average values).

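### SAP 4.1 prints the LDL-C reagent equation solved for the 3rd-generation value, the reverse of its stated use; and, if the page matches the extracted text, SAP 4.1.3 misplaces the creatinine unit factor (both minor)

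*SAP*

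**What the plan says.** **LDL-C.** SAP 4.1 records a change of LDL-C reagent during the study that affects post-baseline values, and requires that "all post-baseline LDL-C related analysis will be performed on two sets of data": as collected and converted. In the converted set, values from 8 March 2018 onward "are converted to 2nd generation values using the formula $X=0.0626+0.882*Y$, where X is the LDL-C value (in SI units, mmol/L) using 3rd generation reagent"; the sentence goes on to say that "Y is the LDL-C value using 2nd generation reagent". It refers to Appendix E for details. In the text available here, Appendix E is only a heading and a file name.

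SAP 4.3.5 sets the roles of the two sets: "the converted values will be considered as the secondary endpoint while the collected values will be used for supportive analysis". SAP 3.1.2 and 4.3.4 agree that the endpoint uses converted LDL-C. For the time-weighted average, SAP 4.1.6 says: "This will be calculated for both sets of LDL-C values (collected and converted) described in section 4.1". The exploratory LDL-C groups in SAP 4.3.8 are defined "for only the converted LDL-C values, as described in section 4.1".

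**Creatinine clearance.** SAP 4.1.3, as extracted, shows a fraction with (140 - age) × weight on top and 72 (men) or 85 (women) × creatinine in µmol/L below. The fraction closes, and the factor 0.01131 follows it. SAP Table 1 uses the result at baseline, both as a continuous variable and in categories, the lowest being below 30 ml/min (severe impairment).

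**The concern.** The LDL-C sentence asks for a 2nd-generation value from a 3rd-generation reading, but the equation has the 3rd-generation value on the left and needs the 2nd-generation value as input. A programmer can follow the labels and invert it. A programmer can also take the sentence at its word, treat the equation as the conversion, and put the reading into the right-hand side. The readable text has neither the solved form nor a worked value to check against. At stake is the size of the LDL-C effect in a named secondary endpoint, and the allocation of rosuvastatin subjects to the exploratory groups cut at 70 and 100 mg/dL.

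For creatinine clearance, a factor that converts µmol/L to mg/dL has to act on creatinine. Placed after the fraction, it multiplies a result that it should divide.

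**Working it through.** **LDL-C: the two uses**

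Inputs: intercept 0.0626, slope 0.882 and the X and Y labels (SAP 4.1). For a 3rd-generation reading r in mmol/L:

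- Inverted, by the printed labels: (r - 0.0626)/0.882. For r = 2.0: 1.9374/0.882 = 2.197.
- Direct substitution: 0.0626 + 0.882 × r. For r = 2.0: 0.0626 + 1.764 = 1.827.

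The two agree only at 0.0626/(1 - 0.882) = 0.53 mmol/L. The slope on r is 1/0.882 in one and 0.882 in the other, so a between-group difference in directly substituted values is 0.882² = 0.778 times the difference in inverted values.

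**Effect on percent change (illustration)**

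Assumptions: baseline 3.5 mmol/L on the 2nd-generation scale (inside the entry range of 3.1 to <4.9), no true change on placebo, a true 50% reduction on rosuvastatin, printed labels correct, every final value after the switch.

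| | Placebo | Rosuvastatin | Difference in percent change |
|---|---|---|---|
| True value = inverted | 3.500 (0.0%) | 1.750 (-50.0%) | -50.0 |
| As collected, 0.0626 + 0.882 × true | 3.150 (-10.0%) | 1.606 (-54.1%) | -44.1 |
| Direct substitution of the reading | 2.841 (-18.8%) | 1.479 (-57.7%) | -38.9 |

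Check: 50 × 0.882 = 44.1 and 50 × 0.778 = 38.9.

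If the labels are swapped, direct substitution is the right step and recovers -50.0. The as-collected difference is then -50/0.882 = -56.7, and inversion gives -50/0.778 = -64.3. The error would run the other way.

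**Share of values converted**

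The documents do not give it. A completer's week-104 visit falls after 8 March 2018 if randomization was after about 10 March 2016 (104 weeks earlier), and Protocol 9.3 plans the study from 3Q 2015 to 1Q 2019. With labels correct and the same share in both arms, the gap between the two uses is 11.1 points × share: 2.8, 5.6, 8.3 and 11.1 points at 25, 50, 75 and 100%.

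**Exploratory cut points**

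Using the protocol's pairing of 120 mg/dL with 3.1 mmol/L, 70 mg/dL is 1.808 and 100 mg/dL is 2.583 mmol/L. A single reading reaches 70 mg/dL at 1.658 (inverted) or 1.979 (direct), and 100 mg/dL at 2.341 or 2.858. Readings between each pair are classed differently. A time-weighted average that includes values from before the switch is affected less.

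**Creatinine clearance**

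The protocol's creatinine exclusion pairs 2.0 mg/dL with 177 (unit printed as mmol/L). 2.0/177 = 0.0113, so 0.01131 is the µmol/L to mg/dL factor. For an assumed man of 60 years, 70 kg, 80 µmol/L:

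- As extracted: 80 × 70/(72 × 80) × 0.01131 = 0.9722 × 0.01131 = 0.011 ml/min.
- Factor beside creatinine: 0.9722/0.01131 = 86.0 ml/min.

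The ratio is 1/0.01131², about 7,818, for men and women alike. As extracted, even a man of 45 weighing an assumed 150 kg would need creatinine of 95 × 150 × 0.01131/(72 × 30) = 0.075 µmol/L or less to reach 30 ml/min. Every real subject would be classed as severe impairment.

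**The case against.** The best defence on LDL-C is that nothing is undetermined. The SAP states the direction of conversion, defines both symbols, gives units and a date, and points to Appendix E. A programmer who respects the labels has one solution. Both sets of values are analysed, and the primary CIMT analysis does not use LDL-C.

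Much of this stands: the equation is coherent, and no value is shown to be wrong. It does not remove the point. The rule for the endpoint is printed in the form that invites the other use, and coherence does not show that the labels themselves are right. Comparing converted with collected results would show which way the program went, but not which way was correct. The collected analysis is only supportive, and SAP 4.3.8 does not use it. Appendix E may settle the matter for those who hold it; nothing is inferred here from its being unreadable.

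On creatinine clearance, the fraction may simply have been closed in the wrong place when the PDF was read, and results near 0.01 ml/min would be noticed at once. Both are fair, so this part is conditional on the page layout.

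**Conclusion.** Minor, but worth correcting. In SAP 4.1 the LDL-C equation runs opposite to its stated use, and the two ways of applying it differ materially: 2.20 against 1.83 mmol/L for a reading of 2.0, and a factor of 0.778 in between-group differences of converted values. The -50.0, -44.1 and -38.9 points rest on the stated assumptions, including correct labels and all final values after the switch.

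A reader might infer that the LDL-C effect will be understated, or that the reagent shift will be applied twice. The documents do not support that. It needs both correct labels and direct substitution; the first cannot be confirmed from the readable text and the second is not shown to have happened. With swapped labels the risk reverses. The consequence is confined to the LDL-C secondary endpoint, its time-weighted average and the exploratory LDL-C groups.

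A reader might also conclude that the creatinine clearance formula is certainly wrong. It is wrong as extracted; whether it is wrong on the page has to be confirmed. It feeds only the descriptive baseline table, and no eligibility or safety rule using creatinine clearance was found.

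**What to change.** 1. **LDL-C.** Check the X and Y labels against the Appendix E report. Then print a single equation solved for the 2nd-generation value. With the labels as printed it is LDL(2nd) = (LDL(3rd) - 0.0626)/0.882. Add one worked value (by those labels, 2.0 mmol/L becomes 2.20) and check the derivation program against it.
2. **Creatinine clearance.** Confirm the layout in the SAP as issued. If it is as extracted, print (140 - age) × weight/(72 × creatinine × 0.01131) for men, with 85 for women, and check the program.

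Cost: at most two corrected rules in the SAP and a check of two derivation programs. No new data are needed.
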